At Week 14, subjects will return for vital signs, study product administration, assessment of concomitant medications, adverse events, and pregnancy test (if applicable).

At Week 16, subjects will return for assessment of regrowth pattern, SALT scoring, AASIS, AA-QoL, SCORAD, EASI and IGA scores (in subjects with AD only), clinical photography, vital signs, study product administration, assessment of concomitant medications, adverse events, and pregnancy test (if applicable).

At Week 18, subjects will return for vital signs, study product administration, assessment of concomitant medications, adverse events, and pregnancy test (if applicable).

applicable).

At Week 20, subjects will return for assessment of regrowth pattern, SALT scoring, AASIS, AA-QoL, SCORAD, EASI and IGA scores (in subjects with AD only), clinical photography, vital signs, study product administration, assessment of concomitant medications, adverse events, and pregnancy test (if applicable).

At Week 22, subjects will undergo vital signs, assessment of concomitant medications, adverse events, pregnancy test (if applicable), and the final study product administration.

At Week 24, subjects will undergo limited physical examination, assessment of regrowth pattern, SALT scoring, AASIS, AA-QoL, SCORAD, EASI and IGA scores (in subjects with AD only), vital signs, clinical photography, assessment of concomitant medications, assessment of adverse events, and blood tests for chemistry and hematology, mechanistic studies, RNA, proteomic analysis, anti-drug antibody (ADA) measurement, and serum tralokinumab levels. In addition, biopsies of the scalp (one biopsy close to the area that was biopsied at Baseline) and skin (in subjects with AD only, one biopsy close to the area that was biopsied at Baseline) will be performed.

Follow-up visits will be conducted at Weeks 32 and 40 for safety analysis, at which the following will be performed: limited physical examination, assessment of regrowth pattern, SALT scoring, AASIS, AA-QoL, SCORAD, EASI and IGA scores (in subjects with AD only), clinical photography, and assessment of concomitant medications and adverse events. In addition, at Week 32 only, blood tests for chemistry and hematology, and an ECG will be performed.

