If a subject is being discontinued prior to Week 24, the following procedures should be performed for the Early Termination visit: limited physical examination, pregnancy test (if applicable), assessment of regrowth pattern, SALT scoring, AASIS, AA-QoL, SCORAD, EASI and IGA scores (in subjects with AD only), clinical photography, assessment of concomitant medications, assessment of adverse events, and blood tests for chemistry and hematology, mechanistic studies, RNA, proteomic analysis, anti-drug antibody (ADA) measurement, and serum tralokinumab levels. In addition, biopsies of the scalp (one biopsy close to the area that was biopsied at Baseline) and skin (in subjects with AD only, one biopsy close to the area that was biopsied at Baseline) will be performed.

If a subject is being discontinued prior to Week 40 (but has completed Week 24), the following procedures should be performed for the Early Termination visit: limited physical examination, ECG (if not completed at Week 32), assessment of regrowth pattern, SALT scoring, AASIS, AA-QoL, SCORAD, EASI and IGA scores (in subjects with AD only), clinical photography, assessment of concomitant medications, assessment of adverse events, and blood tests for chemistry and hematology.

Subjects will not receive any other active treatment for alopecia areata or atopic dermatitis (outside of the study drug) while participating in the study.

Safety, laboratory, and clinical assessments will be performed at specified clinic visits. A

serum pregnancy test will be performed at Screening and urine pregnancy tests will be performed at Baseline and every 2 weeks prior to administration of the IP dose, if applicable.

Biopsies from the scalp will be performed on all subjects at Baseline and Week 24 or Early Termination visit. At Baseline, biopsies will be obtained from involved and uninvolved areas of the scalp. At Week 24 or Early Termination visit, the biopsy will be performed in the vicinity of the involved area biopsied at Baseline. An optional biopsy will be performed at Week 12, close to the area that was involved and biopsied at Baseline.

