37. Non-leukocyte depleted whole blood transfusion within 120 days of genetic sample collection.

SAFETY OF TRALOKINUMAB

Several trials have been conducted with tralokinumab in people with Asthma, Ulcerative Colitis, Idiopathic Pulmonary Fibrosis and in Healthy Volunteers. This is the first time that tralokinumab has been given to subjects with alopecia areata.

In the largest study of tralokinumab to date, a total of 452 subjects with severe, uncontrolled asthma were given tralokinumab 300mg or placebo as an injection under the skin over a 52-week dosing period. Half of the subjects received 300mg tralokinumab or placebo every 2 weeks for the entire study, whereas the other half received 300mg tralokinumab or placebo every 2 weeks for the first 12 weeks, and then every 4 weeks for the rest of the study. Overall, 301 subjects received tralokinumab and 151 subjects received placebo. Side effects occurring more frequently in subjects receiving tralokinumab (5% more frequently) were injection site redness and allergic rhinitis or "hay fever". Other side effects such as asthma, cold-like symptoms, bronchitis, flu-like illness and headache were common in both the placebo and tralokinumab groups. Injection site reactions were experienced by subjects in all groups, but those receiving tralokinumab every 2 weeks experienced reactions the most frequently (35 of 150 subjects [23%] compared to 7 of 76 subjects [9.2%] receiving placebo every 2 weeks). The most common types of symptoms experienced at the injection site in all groups were pain, itching, redness and rash. Three subjects receiving tralokinumab (out of a total of 301) stopped receiving study drug due to reactions at the injection site (redness, rash and urticaria or "hives"). The reactions in all 3 subjects were mild to moderate in severity and occurred after they had received more than one dose of tralokinumab.

The safety of tralokinumab has been tested in monkeys following intravenous (directly into the bloodstream) and subcutaneous (under the skin) administration at doses higher than those being used in this study. No toxic effects were seen following weekly intravenous doses of tralokinumab for up to 6 months of dosing.

ADVERSE EVENTS

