During a previous study where 301 subjects with asthma were given tralokinumab, the following side effects were reported (greater than or equal to 10% occurrence): asthma, nasopharyngitis (cold symptoms), bronchitis, upper respiratory tract infection, and headache. Similar frequencies of side effects were seen in subjects receiving placebo.

Events that were judged to be related to the study drug by the investigator were primarily injection site reactions (redness, itching and pain). There have also been occasional reports of serious side effects in people participating in clinical studies with tralokinumab, but it has not been established that the study drug caused these effects.

There is a small chance of anaphylaxis to tralokinumab. Such reactions have been observed following the use of antibodies to treat human diseases, including asthma; such reactions have been described as occurring rarely (likely to affect fewer than 1 in every 1000 subjects). Anaphylaxis may cause a serious drop in blood pressure; wheezing; difficulty in breathing; a feeling of dread; swelling around the mouth, throat, or eyes; a fast pulse; sweating; severe hives (itchy rash); and sometimes death. Subjects will be monitored after administration of the study drug, and will have medications available to treat any allergic reactions that might occur. Less serious allergic reactions, such as skin rash with or without itching and swelling, may also occur within hours to days after receiving the drug. These effects usually get better without treatment. One person with asthma experienced a rapid allergic reaction known as an acute hypersensitivity reaction (increased wheezing, shortness of breath and facial swelling) after being given tralokinumab intravenously, i.e. administered through the vein.

Additional potential risks include the development of anti-drug antibodies. Anti-drug antibodies could result in an immune complex disease that can include symptoms such as joint pain, serum-sickness, inflammation of arteries and veins called vasculitis, autoimmunity, or it can change the amount of drug in blood or the way the drug works.

Other potential risks include an increased risk for tumors, such as breast cancer and prostate cancer, and an increased risk for severe infections like opportunistic infections and parasitic worm infection. These side effects have not been seen in other tralokinumab studies.

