The effects of tralokinumab on the unborn fetus are not known. Some drugs cause premature birth or birth defects. There is a potential risk of miscarriage with tralokinumab though this has not been seen in animal studies. In the Tralokinumab Asthma Study five pregnancies were reported. Of these, four mothers and one father were taking part in the Tralokinumab Asthma Study. One of these four mothers who was taking part in the Tralokinumab Asthma Study had a miscarriage. However, this mother was found to be taking placebo and so this miscarriage was not related to tralokinumab.

It is very important that women taking part in the study practice birth control to prevent pregnancy during this study. The acceptable methods of birth control have been

described previously in this document. Women who are pregnant or nursing mothers are not allowed to be in the study as the safety of tralokinumab administration during pregnancy and to nursing children is unknown. Women who become pregnant during the study will have to terminate the study. The study doctor or study staff may ask for information about the pregnancy and the child's health at birth and may share this information with the sponsor.

There may be other side effects of tralokinumab that are unknown, which include the condition getting worse. Subjects will be monitored by the Study Doctor and, in the event that the results show conditions that may need following, the subject will be followed by the Study Doctor, their own doctor, or a specialist. This may require the release of records to a non-study doctor. In this case, subjects will be asked for their consent (permission).

It is possible that receiving tralokinumab may change how subjects' regular medications, vaccines, or supplements work. Subjects will be asked to tell the Study Doctor about any medications, supplements, or vaccines before taking them during the study.

SAFETY MONITORING

The study will be conducted in accordance with our department's Standard Operating Procedures, which are based on US FDA Title 21 Code of Federal Regulations and ICH Good Clinical Practice guidelines.

An investigator will review all laboratory results and assess for adverse events. The principal investigator will be informed of all adverse events. In the event that a subject's safety is compromised, the investigator will discontinue the subject immediately.

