The Principal Investigator will provide safety data to an independent Data and Safety Monitoring Board every 12 months. This DSMB will be comprised of board certified dermatologists who are not directly related to this study. The DSMB will review the data and provide a report of their findings to the Principal Investigator.

EARLY TERMINATION

Any individual whose health or well being may be threatened by continuation in this study will be discontinued by the investigator.

If a female subject becomes pregnant at anytime during the study, she will be discontinued immediately. She will be asked to provide the investigator with medical updates throughout her pregnancy and on the final outcome of the pregnancy.

Any subject who chooses to discontinue the study, or is discontinued from the study by the investigator will be asked to return for a final Early Termination visit for the procedures listed in the Schedule of Events table.

Considering there is no current treatment that is very effective in treating alopecia areata, these subjects are highly motivated to participate in any study that may provide a treatment option. Thus, we have accounted for a 10% drop out rate, and plan to enroll 30 subjects in order to have 27 subjects complete the study.

INVESTIGATIONAL DRUG SUPPLY

In this double-blind study, the investigator will supply tralokinumab (formulated at 150 mg/ml in an isotonic sodium acetate buffer at pH 5.5 in accessorized prefilled syringes for subcutaneous injection) 300 mg for up to 20 subjects and placebo for up to 10 subjects. The tralokinumab and placebo will be provided by MedImmune as 150 mg tralokinumab (and matching placebo) prefilled syringes. Both the 150 mg tralokinumab and the matching placebo prefilled syringes will be of the same quality and identical in size and shape. All study medication will be stored in a secure cool area between 2-8°C. Study drug will be administered to subjects at each visit, and any unused study drug will be kept at the study site. The number of missed doses will be documented for each subject. The investigative site will account for all study drug dispensed and stored during the study.

EFFICACY EVALUATIONS

The following efficacy parameters will be obtained at the previously specified visits:

1. Investigator evaluation of alopecia on the scalp (efficacy of the drug) using the following tools:

Severity Alopecia Tool (SALT)⁵ score:

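### Subjects who stop before Week 24, including those removed for safety, have no scheduled safety follow-up after one exit visit, while completers are seen up to 18 weeks after their last dose

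*Combined protocol and SAP*

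**What the plan says.** For completers, the Week 22 entry in Study Design ends with "and the final study product administration". A full assessment follows at Week 24, and then: "Follow-up visits will be conducted at Weeks 32 and 40 for safety analysis". Both follow-up visits include a limited examination, adverse events and concomitant medications. Chemistry, hematology and an ECG are added at Week 32 only.

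For early stoppers, Study Design states: "If a subject is being discontinued prior to Week 24, the following procedures should be performed for the Early Termination visit". The list that follows is a proper post-dose check: examination, adverse events, safety bloods, anti-drug antibodies (ADA) and drug level. The Early Termination section says that a subject who chooses to leave, or whom the investigator takes out, "will be asked to return for a final Early Termination visit". No interval from the last dose is given. Neither the visit text nor the Schedule of Events sends these subjects to Week 32, to Week 40, or to any visit counted from their own last dose. No route is described for stopping the drug while staying in follow-up.

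Two rules move subjects with safety problems into this group. Early Termination says: "Any individual whose health or well being may be threatened by continuation in this study will be discontinued by the investigator". Safety Monitoring says that when a subject's "safety is compromised, the investigator will discontinue the subject immediately".

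**The concern.** By scheduling two visits after dosing for the stated purpose of safety, the plan itself treats that period as one that needs observation. It then leaves those visits out for a group that contains, by rule, the subjects taken off drug because of harm or feared harm. Someone removed for safety after a few doses has less scheduled safety observation than someone who tolerated the full course.

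Safety in alopecia areata, with and without atopic dermatitis, makes up two of the four secondary objectives. The section on the drug's safety notes: "This is the first time that tralokinumab has been given to subjects with alopecia areata". The Adverse Events section lists potential risks that need not show themselves on the day of exit. For example, "Anti-drug antibodies could result in an immune complex disease", and severe infection is also named. The documents give no onset times, so how many such events would fall after exit cannot be estimated. What can be said is that the plan does not look for them.

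**Working it through.** **Inputs**
- Last dose for completers: Week 22 (Study Design and Schedule of Events).
- Assessments after it: Weeks 24, 32 and 40 (same places).
- Early stoppers: one Early Termination visit, timing not stated (Study Design; Early Termination).
- Drop-out 10%, 30 enrolled, 27 completing (Early Termination).
- Allocation 2:1, up to 20 on tralokinumab and 10 on placebo (Investigational Drug Supply).
- Assumption, not in the documents: the exit visit falls 0 to 4 weeks after the last dose.

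**The plan's own figure.** 27 / (1 − 0.10) = 30 enrolled. This reproduces.

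**Scheduled safety assessments after the last dose**

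| | Completer | Stops before Week 24 |
|---|---|---|
| Weeks after last dose | 24 − 22 = 2; 32 − 22 = 10; 40 − 22 = 18 | one visit, interval not stated |
| Number | 3 | 1 |

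**Unobserved time per early stopper**, against the 18 weeks given to completers: 18 − 4 = 14 to 18 − 0 = 18 weeks.

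**Subjects affected.** 10% × 30 = 3, of whom 2/3 × 3 = 2 are on drug and 1 on placebo if drop-out is equal by arm. This is a ceiling at the planned rate, because the 10% covers drop-out from the whole study and some subjects may leave after Week 24. If drop-out were 20% or 30% (an assumption for range), the count would be 6 or 9. The number who would stop for safety is not given.

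**Total.** 3 × 14 = 42 to 3 × 18 = 54 subject-weeks, out of 30 × 18 = 540 planned. 42/540 = 7.8% and 54/540 = 10.0%. These totals inherit the same ceiling.

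**Does other text fill the gap?**
- Safety Monitoring and the end of Adverse Events provide follow-up for a condition that results have already revealed, possibly by a non-study doctor. It is conditional and has no timetable.
- Early Termination asks for pregnancy updates through to outcome. That covers pregnancy only.
- The Data and Safety Monitoring Plan requires serious events to be reported within 24 hours once the site knows of them. It does not make the site ask.

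None of these schedules a search for new events after exit.

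**Sensitivity to the last-dose week.** One sentence in Study Design has injections running through Week 24. If that were right, completers would be seen 32 − 24 = 8 and 40 − 24 = 16 weeks after the last dose, and the contrast would stand.

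**A related window.** Contraception is required for 16 weeks after the last dose, which for a completer ends at 22 + 16 = Week 38, inside follow-up. An early stopper has no scheduled contact covering that window. No pregnancy test is planned at Week 32 or 40 for anyone, so the difference lies in contact and adverse-event enquiry, not in testing.

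**The case against.** The strongest reply is that the gap is small and partly covered. A subject removed for a recognised problem may well have a condition that triggers the as-needed follow-up, and pregnancy is followed to outcome. The exit visit already carries the Week 24 bloods, ADA and drug level. Weeks 32 and 40 repeat neither ADA nor drug level for anyone, so counting three visits against one overstates what is lost on the antibody risk in particular. The trial is a 30-subject exploratory pilot with a biopsy-marker primary endpoint. No estimate, test or sample size depends on this point, and at the planned drop-out rate about two drug-treated subjects are concerned. The departmental Standard Operating Procedures cited under Safety Monitoring might also set follow-up after withdrawal.

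Much of this stands as a limit on size. The gap concerns new or late events after exit, not problems already known at exit. The totals are upper limits, and subjects who withdraw consent cannot be recovered at all. For immune-complex disease, the later visits would add symptoms, examination and limited laboratory data, not antibody monitoring.

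It does not remove the point. A single exit visit cannot record what happens after it, and follow-up of known conditions is not enquiry about new ones. The departmental procedures are not available, so they cannot be counted as filling the gap. In a study this small, each safety removal also carries a large share of the safety information.

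**Conclusion.** The concern holds. The plan observes completers to 18 weeks after the last dose and schedules nothing beyond one exit visit of unstated timing for subjects who stop before Week 24, a group that includes safety removals by rule. At the planned drop-out this affects at most about 3 of 30 subjects and 8 to 10% of post-dose subject-weeks, assuming an exit visit 0 to 4 weeks after the last dose.

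The consequence is incomplete safety observation. The same rule applies in both arms, and stop rates by arm and cause are not given, so no direction of bias between arms can be claimed. The point should be corrected because the remedy is cheap and protects subjects. It does not threaten the primary endpoint.

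**What to change.** State that stopping study drug is not the same as leaving the study. After the Early Termination visit, every subject who received at least one dose and has not withdrawn consent attends two safety visits, 10 and 18 weeks after their own last dose, with the Week 32 and Week 40 content. If a visit is declined, adverse events and medications are taken by telephone at that time.

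Examples: a last dose at Week 4 gives visits at 4 + 10 = Week 14 and 4 + 18 = Week 22. A last dose at Week 20 gives Weeks 30 and 38. The latest possible case is 22 + 18 = Week 40, so the study is not lengthened. These visits serve safety follow-up and do not replace the Week 24 efficacy assessment.

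The cost is at most about 2 × 3 = 6 extra visits at the planned drop-out, in a format that already exists, plus amendment and consent wording. Some subjects will decline, and a telephone check provides no examination, bloods or ECG.

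One separate wording correction can go in the same amendment. The list of pre-Week 24 Early Termination procedures in Study Design omits the ECG, which footnote 6 of the Schedule of Events already requires, so it should be added to the list.

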**A randomized placebo-controlled single center pilot study of the safety and
efficacy of tralokinumab in subjects with moderate to severe alopecia areata**

PI: [name]

NCT02684097

Document date: 8-11-2015

A randomized placebo-controlled single center pilot study of the safety and efficacy of tralokinumab in subjects with moderate to severe alopecia areata

PI: [name]

NCT02684097

Document date: 8-11-2015

A randomized placebo-controlled single center pilot study of the safety and efficacy of tralokinumab in subjects with moderate to severe alopecia areata

Institution:

Icahn School of Medicine at Mount Sinai
Department of Dermatology

[REDACTED], [name]
[name]
[contact]
[contact]

Investigators:

Principal Investigator:
[name], PhD

Co-investigators:
[name]

Protocol Version: April 21, 2015

Amendment # 1: August 11, 2015

Amendment #2: September 30, 2015

HYPOTHESES:

Primary Hypothesis:

1. It is hypothesized that IL-13 is involved in the pathogenesis of alopecia areata (AA).

Secondary Hypothesis:

1. Tralokinumab is superior to placebo for induction of hair regrowth in patients with moderate to severe alopecia areata, and will result in improved clinical outcomes for subjects with concomitant atopic dermatitis (AD).

OBJECTIVES and ENDPOINTS:

Primary objective

- 1) This is a pilot study intended to look at IL-13 associated cellular and molecular markers in the skin of patients with alopecia areata and to gain some insight into whether blocking IL-13 with Tralokinumab will affect those markers and hair regrowth

Secondary objectives

- 1) To study the safety of tralokinumab in patients with moderate to severe alopecia areata.
- 2) Study the safety of tralokinumab in patients with concomitant moderate to severe alopecia areata and atopic dermatitis.
- 3) Study the mechanism of action of tralokinumab in patients with moderate to severe alopecia areata.
- 4) Study the mechanism of action of tralokinumab in patients with concomitant moderate to severe alopecia areata and atopic dermatitis.

Primary endpoints

- 1) Change from baseline in cellular, and molecular markers in skin biopsies after treatment.

Secondary endpoints

- 1) Percentage change from Baseline in the Severity of Alopecia Tool (SALT) at Week 24.
- 2) Percentage of patients achieving 50% or greater improvement in their SALT score (SALT₅₀) at Week 24, compared to Baseline.

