Fig 1. Figure 1 shows comparable cytokine expression of the defining Th2 cytokine/IL-13, the defining Th1 cytokine/IFN gamma, and the Th17/IL-23 cytokines/IL-17A and IL12/23p40 in AA and AD. Lesional psoriasis skin tissues show a significantly higher expression of both IL-17A and IFN gamma, with significantly lower expression of IL-13 as compared with both AA and AD. Significant decreases in mRNA expression of IL-13, and IL12/23p40 are seen after treatment with intralesional corticosteroids, without significant changes in the other cytokines. P value= 0.0002 for the IL-13, and p=0.1 for the IFN gamma lesional vs non-lesional alopecia skin comparisons. JAK3 shows similar activation in AA, AD, and Psoriasis. NL- non lesional skin from scalp of AA patients; L- lesional skin from scalp of AA patients; PTX- post intralesional steroid treatment skin from scalp of AA patients; PS-psoriasis lesional skin; AD- AD lesional skin. N=6 patients for both NL and L, and 4 for PTX.

STUDY DESIGN:

This is a randomized, double-blind, placebo-controlled pilot study of a total of 30 subjects with moderate to severe alopecia areata involving 30-100% of the scalp. We expect 50% of these subjects to have concomitant alopecia areata (AA) and atopic dermatitis (AD).

Subjects with AA alone (15 subjects) will be randomized (2:1) to either receive tralokinumab 300 mg (150 mg/ml) or placebo via subcutaneous injection using 2 pre-filled syringes Q2W for 24 weeks. Subjects with concomitant alopecia areata and atopic dermatitis (15 subjects) will be randomized separately in a 2:1 ratio to receive tralokinumab 300 mg (150 mg/ml) or placebo via subcutaneous injection using 2 pre-filled syringes Q2W for 24 weeks.

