Prior to beginning this study, approval for all study related documents (protocol, consent form, advertising) would be obtained from the Icahn School of Medicine at Mount Sinai Program for the Protection of Human Subjects (Institutional Review Board), [name].

DATA ANALYSES:

This is an exploratory study therefore sample size has been kept relatively low. Data collected from this study will be used to obtain estimates of differences and variability, of the change in treatment for IL-13. If the variability of the Post vs Pre differences are of the magnitude of the LS vs NL differences observed in preliminary data (SE=0.46) then the size of the confidence interval in differences could be observed in this study would be 0.58. As for the secondary outcome, the spontaneous regrowth rate in alopecia areata is 4%. To demonstrate efficacy of the study drug, a response rate of at least 50% is required. To be statistically significant, we would require a minimum of 10 subjects in the study, with an expected response rate of 0 or 1 subject in the placebo group.

MECHANISTIC STUDIES DATA ANALYSES:

For the comparisons of expression levels of lesional, and non-lesional AA skin, we will use RT-PCR, and gene-arrays. RT-PCR values will be normalized to the housekeeping gene hARP (validated in all our AD studies) and log2-transformed prior to analysis. Microarray data will be preprocessed using standard pipeline (exhaustively used by our group in a large number of studies) and log-2 transformed expressions. Adjustments by batch effect and clinical variables will be carried out if needed using ComBat. Mixed effect model on R's *limma* framework will be used and p-values for the moderated t-tests and paired-t-test will be adjusted by Benjamini-Hochberg procedure.

Extensive bioinformatics tools will be employed to gain insights on the results and test hypotheses that are generated in the "data mining stage". This will include (but is not be limited to) pathway and gene-set enrichment analyses using Ingenuity software, GSEA, the R package GSVA (Gene Set Variation Analysis) and other in-house codes produced by our group.

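### Testing ComBat-adjusted array data can make p-values too small or remove real effect, depending on settings the plan does not state; batch belongs in the limma model

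*Combined protocol and SAP*

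**What the plan says.** Mechanistic Studies Data Analyses gives the array pipeline in three steps: preprocessing and log2 transformation; then "Adjustments by batch effect and clinical variables will be carried out if needed using ComBat"; then "Mixed effect model on R's *limma* framework will be used", after which "p-values for the moderated t-tests and paired-t-test will be adjusted by Benjamini-Hochberg procedure". The comparison named at the start of that section is between lesional and non-lesional skin: "For the comparisons of expression levels of lesional, and non-lesional AA skin, we will use RT-PCR, and gene-arrays". The primary endpoint, under Objectives and Endpoints, is a pre/post quantity: "Change from baseline in cellular, and molecular markers in skin biopsies after treatment".

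The plan does not say:
- what would trigger the adjustment;
- which clinical variables are meant;
- which terms ComBat would be told to preserve;
- which terms enter the limma model;
- what false discovery rate applies;
- how samples are assigned to array batches.

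Biopsy Specimens says only that samples may be held in storage, and leaves tissue handling to the laboratory's own procedures.

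**The concern.** ComBat estimates batch effects from the data and subtracts them. If the corrected values are then tested as raw data, the second step does not know that batch terms were estimated. It charges no degrees of freedom for them and ignores the information lost where batch and the tested factor overlap. There are two cases.

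- **Tested factor protected** (listed in ComBat as a term to preserve): the estimate is sound, but its standard error is too small.
- **Tested factor not protected**: ComBat takes part of the real difference for batch and removes it.

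The Benjamini-Hochberg procedure does not repair p-values that are wrong on entry. The same section then sorts biomarkers by whether they show significant group differences and models disease activity and response, so errors could carry forward. Baseline and Week 24 biopsies are about six months apart, and nothing in the plan requires a subject's samples to be run together.

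**Working it through.** The plan gives no figure to reproduce, so the check is a simulation plus a hand calculation.

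**Inputs from the documents.** Under Early Termination the plan is to "plan to enroll 30 subjects in order to have 27 subjects complete the study". Randomization is 2:1 (Study Design), so 27 × 2/3 = 18 completers on active drug and 9 on placebo. Pairs arise within subjects: "At Baseline, biopsies will be obtained from involved and uninvolved areas of the scalp", with a further biopsy near the involved site at Week 24.

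**Assumptions.** Two or three batches; batch-effect SD 0.8 against a residual SD of about 1; within-subject correlation 0.4; two-sided 0.05; Benjamini-Hochberg at 5%. It is also assumed that the array pipeline serves the pre/post comparison, since the section names only lesional v non-lesional.

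**Method.** 1,000 null genes, 60 to 120 replicates, parametric empirical-Bayes ComBat, limma moderated t, and an estimated common within-subject correlation for paired layouts. Rejection rates at nominal 0.05:

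| Layout | ComBat, factor protected | ComBat, not protected | Batch in limma model |
|---|---|---|---|
| Arms 18:9, three balanced batches | 0.074 | 0.058 | 0.050 |
| Arms, mild imbalance (10/8 v 4/5) | 0.064 | 0.052 | 0.050 |
| Arms, moderate (12/6 v 3/6) | 0.075 | 0.045 | 0.050 |
| Arms, severe (15/3 v 2/7) | 0.121 | 0.022 | 0.050 |
| Pre/post split 60% | 0.062 | 0.050 | 0.049 |
| Pre/post split 80% | 0.180 | 0.035 | 0.050 |
| Pre/post split 90% | 0.292 | 0.019 | 0.050 |
| Lesional v non-lesional, pair in one batch | 0.056 | 0.051 | 0.051 |
| Arm by time, subject in one batch, arms 12/6 v 3/6 | 0.054 | 0.051 | 0.050 |

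With the factor protected, the chance of any false discovery under the complete null reached 0.63 (severe arm imbalance) and 1.00 (80% and 90% pre/post splits). With batch in the model it was 0.02 to 0.04 in those layouts and at most 0.07 in any. A repeat under the same assumptions gave 0.06 to 0.27 across uneven layouts with the factor protected, and 0.048 to 0.052 with batch in the model.

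**Effect removed when the factor is not protected.** For location-only correction the retained fraction is f = [Σ over batches of n1·n0/(n1+n0)] ÷ [N1·N0/(N1+N0)], where n1 and n0 are the numbers in the two groups within a batch, and N1 and N0 the totals.

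- Severe arm layout: (15×2/17 + 3×7/10) ÷ (18×9/27) = 3.865/6 = 0.64.
- Pre/post 80%, that is 22/5 and 5/22: (2 × 22×5/27) ÷ (27×27/54) = 8.148/13.5 = 0.60.
- Pre/post 90%, that is 24/3 and 3/24: (2 × 24×3/27) ÷ 13.5 = 5.333/13.5 = 0.40.

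So a true difference of 1.0 becomes about 0.4 to 0.6. The smallest value in simulation was 0.39.

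**Why protection inflates.** The same f measures the information left after batch. The second step uses a standard error too small by √f. For the severe arm layout √0.644 = 0.803, so the 25-df critical value of 2.06 acts as 2.06 × 0.803 = 1.65, a two-sided error of about 0.11. The simulated 0.121 is slightly higher because batch scale is also estimated and degrees of freedom are not charged.

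**The case against.** Several points on the other side stand.

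- The step is conditional, and the limma terms are not listed, so a batch term is not excluded.
- Samples may be stored, so a single run, or batches that keep subjects intact, is possible. The laboratory procedures are not available to us.
- If a subject's samples share a batch, batch cancels from paired contrasts and the inflation is negligible (0.054 to 0.056), even with arms unevenly spread.
- ComBat covariates are normally effects to preserve. That the clinical variables would be subtracted is only one reading of the sentence.
- The ComBat sentence follows the microarray text, while RT-PCR has its own housekeeping-gene normalization. The study calls itself exploratory, and its only stated precision aim concerns the change in IL-13.

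A reader might infer that p-values are too small whenever batches are not perfectly balanced. That fails in both directions. Without protection, marked imbalance makes the test conservative (0.019 to 0.035). With protection, perfectly balanced batches of nine still gave 0.074. A reader might also infer that the whole primary endpoint is compromised, but it covers cellular and molecular markers, and only the array part is clearly affected.

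These points limit the concern without answering it. None of the favourable conditions is written into the plan, and an exploratory label does not make a mis-sized p-value usable for sorting biomarkers.

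**Conclusion.** The concern holds conditionally. As ordered, the plan tests ComBat-corrected array values as data. With the tested factor protected and unevenly spread, the error at nominal 0.05 is about 0.06 to 0.29 for visit splits of 60% to 90%, and 0.06 to 0.12 for uneven arms. Without protection, strong imbalance leaves about 0.4 to 0.6 of a true difference. With subjects kept within batches the error is about 0.055.

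The sizes depend on the assumed batch SD, within-subject correlation and layouts. They are a range and do not predict what this trial will show. The 80% and 90% splits are deliberate extremes, though the plan does not rule them out. The direction of the error is undetermined because the plan does not say what ComBat would protect. This is a worthwhile, cheap improvement to the array analysis and does not invalidate the study.

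**What to change.** In Mechanistic Studies Data Analyses, replace the ComBat sentence for testing purposes. Put batch and a named list of clinical covariates in the limma design matrix, with subject as the blocking factor. Use ComBat-adjusted values only for plots and clustering. State the false discovery rate. Add a laboratory instruction to run all of a subject's stored samples in one batch, with arms spread across batches, and record the batch of each sample.

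The cost is a few sentences, a few degrees of freedom, and the loss of some nominally significant genes. Holding Baseline samples until Week 24 delays the arrays. If batch is completely confounded with visit or arm, no analysis can separate them, so the layout must be settled before samples are run.
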